## **2.e Risks and Benefits**

### Risks

There are minimal risks for participants.

The assessment process may carry potential risks. For example, some of the questions may be upsetting to participants, and there may be some risk of breach of confidentiality if the suicide or crisis assessment protocols need to be deployed.

There are no high-risk or hazardous aspects of our proposed mobile intervention program; however, we recognize that programs to treat mental health problems may promote increased focus on mental health symptoms, more than that which may exist before starting the program.

Coaches in SilverCloud Health will be recruited from the institutions of the study team members (i.e., WUSM, PAU, PSU, UM). Coaches will be students in a graduate program in psychology, counseling, or social work. Coaches will be trained and under the close supervision of coach supervisors, at WUSM and PAU, as well as the Fidelity Monitoring Center. Given national data showing that ~10% of students have seriously considered suicide in the past year, suicidality will be consistently monitored throughout the study, including within the program itself and through the completion of all assessments. Students who endorse any suicidality on these assessments will receive immediate follow-up, including a referral to seek in- person care. Participant safety is of utmost clinical import, and several safety procedures will be implemented.

- 1) SilverCloud Health flags and notify coaches when a user responds positively to the PHQ-9 item about suicidality. Coaches will monitor the platform weekly to assess for

---

significant changes in symptoms (e.g., increased purging). Any participant deemed unsafe or needing more intensive clinical intervention will be given a referral by their coach as well as contacted directly via telephone. Appropriate follow-up (e.g., contacting the university's on-call clinical staff or local police) will be implemented if participants are deemed to be at imminent risk and no response is provided by the participant indicating their safety. This protocol is to safeguard against concerns with keeping individuals in guided self-help care when more intensive services are warranted.

2) Individuals who remain in the clinical symptom range, in both the intervention and control conditions, at the 6-month or 2-year follow-up assessments, will be offered a referral for in-person treatment. For individuals in the intervention condition, in line with a stepped care model, those who do not demonstrate symptom improvement by 6 weeks will be referred to in- person care but can still engage in the program.

In the case of imminent risk, such as in the extremely rare case of a user reporting plans of suicide or homicide, there are several steps that coaches are mandated to take as mandated reporters. First, coaches contact a coach supervisor and the Fidelity Monitoring Center either by phone or an email marked URGENT to consult about how to proceed as soon as possible. If coaches do not receive a response within an hour, they will reach out to a back-up coach supervisor. Second, coaches identify the appropriate local agency such as the campus police at the user's college or university to prepare for possibly making a report. Next, they provide the user with a variety of emergency options such as counseling center information, suicide hotline phone number, emergency room location, or local police information and encourage clients to seek additional support or hospitalization through these options. Coaches also gather relevant information by reviewing the coaching record for all identifying information available such as name, age, phone number, and email address to provide to the agency when making a report. If it is deemed appropriate by the coaching supervisor, coaches call in the report as soon as possible to the identified local agency. They also follow up with the user, express concern, provide support, and let him/her know a report has been made. In addition, coaches follow up with the coach supervisor and the Fidelity Monitoring Center via email to let him/her know the report was made. Finally, coaches continue to monitor the user for emerging or worsening risks, as demonstrated by information the user inputs into the program or messages to the coach, and they continue to keep in close contact with the coaching supervisor. Should the user continue to worsen and be deemed at continued imminent risk, the coach and coach supervisor may make a decision to withdraw the participant from the program.

In addition, [name] will hold monthly meetings with coach supervisors. Furthermore, the Fidelity Monitoring Center will conduct fidelity checks on the coaching data from SilverCloud Health to ensure that coaches are following protocol (e.g., referrals given if lack of symptom improvement). In general, the Fidelity Monitoring Center will oversee regular review of coaches using quantitative and qualitative metrics that include tone and style (authentic, personalized) of their interactions with clients, content (depth, goal orientation), efficiency (response time), user engagement, outcomes, and accuracy rate for risk management. Coaches that do not meet the metrics will be put on a performance improvement plan and may be terminated if improvement is not demonstrated.

### Benefits

---

The benefits to participants in this study and to society are expected to be great. In terms of potential benefits to participants, these include: improved uptake of services, reduced anxiety, depressive, and/or ED symptoms, and improved quality of life. The treatment may also improve academic impairment and reduce likelihood of dropout from college as well as stress on the individual posed by the burden of mental health problems. In addition, it is possible that skills to solve ongoing problems that may maintain mental health problems may improve. The growing prevalence and burden of mental health problems on the college campus highlight the need for a new approach for detecting mental health problems and engaging college students in services. Therefore, the potential risks that are associated with this study are reasonable when considering the many benefits that the participants and society may gain.

## **2.f Early Withdrawal of Subjects**

The recruitment emails will note that students can reply to decline participation (and any further reminders); they may also select this option on the consent form page of the screening survey.

## **2.g When and How to Withdraw Subjects**

Taking part in this research study is voluntary. Participants may choose not to take part in this research study or may withdraw their consent at any time. They may withdraw by telling the study team they are no longer interested in participating in the study or they may send in a withdrawal letter. There will be no penalty or loss of benefits to which they were otherwise entitled.

## **2.h Data Collection and Follow-up for Withdrawn Subjects**

When a participant withdraws from the study, the research team will stop collecting data from them.

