(excluding anorexia nervosa, for which more intensive medical monitoring is warranted), which account for a substantial proportion of the mental health burden on college campuses, and who are not currently engaged in mental health services (N=7,884; of 146,000 initially screened) will be randomly assigned to: 1) intervention via the mobile mental health platform; or 2) referral to usual care (i.e., campus health or counseling center). Our comprehensive mental health care platform can yield clinical benefit to students, appeal to university stakeholders, minimize barriers to implementation sustainability on campuses, and produce an economic return on investment compared to usual care. This population-level approach to service engagement has the potential to improve mental health outcomes for the 20+ million students enrolled in U.S. colleges and universities.

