In the case of imminent risk, such as in the extremely rare case of a user reporting plans of suicide or homicide, there are several steps that coaches for students engaging in the mobile program are mandated to take as mandated reporters. First, coaches contact a coach supervisor and the Fidelity Monitoring Center either by phone or an email marked URGENT to consult about how to proceed as soon as possible. If coaches do not receive a response within an hour, they will reach out to a back-up coach supervisor. Second, coaches identify the appropriate local agency such as the campus police at the user's college or university to prepare for possibly making a report. Next, they provide the user with a variety of emergency options such as counseling center information, suicide hotline phone number, emergency room location, or local police information and encourage clients to seek additional support or hospitalization through these options. Coaches also gather relevant information by reviewing the coaching record for all identifying information available such as name, age, phone number, and email address to provide to the agency when making a report. If it is deemed appropriate by the coaching supervisor, coaches call in the report as soon as possible to the identified local agency. They also follow up with the user, express concern, provide support, and let him/her know a report has been made. In addition, coaches follow up with the coach supervisor and the Fidelity Monitoring Center via email to let him/her know the report was made. Finally, coaches continue to monitor the user for emerging or worsening risks, as demonstrated by information the user inputs into the program or messages to the coach, and they continue to keep in close contact with the coaching supervisor. Should the user continue to worsen and be deemed at continued imminent risk, the coach and coach supervisor may make a decision to withdraw the participant from the program.

In the case that individuals endorse criteria for possible AN (low weight and significant weight shape concerns) at the 6-month or 2-year follow-up assessments, they will be offered a referral for in-person treatment.

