## 2.a Data Collection Procedures for Adverse Events

For the purpose of this study, adverse events will be defined as unanticipated problems involving risks to the study participant. A serious adverse event will be defined as any untoward occurrence that results in death, is life threatening, or creates persistent and

---

significant disability. The initial step in reporting adverse events of any kind is to consult with [name], PI at PSU, who will be providing oversight for adverse event reporting for the study. Additionally, adverse events will be reported to PIs at the other sites, Drs. [name] (WUSM), [name] (UM) and [name] (PAU), who will decide if the event is serious enough to warrant treatment discontinuation or participant withdrawal. Any potentially adverse events will be evaluated by the PIs within 72 hours. All serious adverse events will be immediately reported to the IRB of Record. All adverse events and study withdrawals, together with a detailed explanation of the event and withdrawal, will be forwarded to the Human Subjects Committee and the DSMB. In addition, at its regular meeting, the DSMB will summarize all adverse events of any severity, to be forwarded to the IRB of Record via [name].

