## ***F3 Analysis Plan***

To evaluate efficacy of the mHealth platform vs. usual care, in engaging participants (Aim 1) we will use hierarchical logistic regression to examine uptake (i.e., individuals beginning any sort of treatment). Outcome will be at least one session of mental health services use (either online or in-person) assessed at 6 weeks, 6 months, and 2 years. Using hierarchical logistic regression, we will also examine efficacy in reducing or preventing number of students with mental health disorders (i.e., a positive screen for at least one of anxiety, depression, or ED as the outcome reflecting a "clinical case") assessed at 6 weeks, 6 months and 2 years, with a primary endpoint of 2 years. This allows for a single, universal outcome applicable to everyone in the study. Both logistic regression models will include random intercepts for colleges and for students nested within colleges, and account for repeated assessments within students, and will estimate the following fixed effects: main effect of time (coded as a factor variable, including baseline, 6-weeks, 6-months, and 2 years), treatment condition, and two-way interaction between time and treatment condition.

To evaluate reduction in disorder-specific symptoms (Aim 2b) and improvement in quality of life (Aim 2c), multilevel models will be used. Analyses of symptom change will be conducted within each clinical disorder subgroup separately with relevant symptoms as the response variables. We will also use a z-score to standardize primary symptom measures to obtain an estimate for a unified intervention effect. All symptom models will include random intercepts for colleges and for students nested within colleges, account for repeated assessments within students, and will estimate the following fixed effects: main effect of time, treatment condition, and two-way interaction between time and treatment condition. Parameter estimates from these models will allow separately

---

comparing change between arms from pre to 6 weeks, pre to 6 months, and from pre to 2-year follow-up. Each model will use dummy-coded factor terms as a stringent test of the treatment to ensure that: 1) treatment was associated with significantly greater change from pre to post than the control group; and 2) gains made in treatment at 6 weeks are maintained and significantly greater than baseline at each follow-up.

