#### ***F4 Missing Outcome Data***

All analyses will be intent-to-treat analyses, using full-information maximum likelihood to handle missing data.

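### Section 2.h stops data collection at withdrawal without separating investigator-initiated withdrawal from withdrawal of consent, so the 2-year outcome can be lost for outcome-related reasons

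*Combined protocol and SAP*

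**What the plan says.** Four parts of the combined protocol and SAP bear on this.

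- **Follow-up after withdrawal.** D2 2.h consists of one sentence: "When a participant withdraws from the study, the research team will stop collecting data from them". It makes no exception and does not distinguish who initiated the withdrawal. The section before it, 2.g, describes only the voluntary route, in which participants "may withdraw their consent at any time".
- **Withdrawal after an adverse event.** E2 2.a has events reported to the site principal investigators, "who will decide if the event is serious enough to warrant treatment discontinuation or participant withdrawal". Stopping treatment and withdrawing the participant are named as alternatives.
- **Removal from the program.** For a user who keeps worsening and remains at imminent risk, D2 2.b says that "the coach and coach supervisor may make a decision to withdraw the participant from the program". Section 2.e repeats this. Neither section says whether such a user still receives the study surveys.
- **Analysis.** F4 states in full: "All analyses will be intent-to-treat analyses, using full-information maximum likelihood to handle missing data". F3 sets the clinical-case outcome "with a primary endpoint of 2 years". No sensitivity analysis for outcome-dependent missingness is planned.

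**The concern.** An intent-to-treat comparison needs outcomes on participants whatever happens to their treatment. If an investigator ends participation because of an adverse event and 2.h then applies, every later survey is lost, and the reason for the loss is plausibly linked to caseness.

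The loss may also be unequal between arms. Coaches work only with intervention participants. They review symptoms weekly, receive flags on the suicidality item and report potential adverse events at once (D2 2.b, D3, E2 2.b). Control participants are seen mainly through the surveys at 6 weeks, 6 months and 2 years, and an event first found at the 2-year survey cannot cost that endpoint. If more true cases drop out of the observed data in the intervention arm, its case proportion looks too low and the comparison tilts in its favour.

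Maximum likelihood protects against this only if missingness depends on data in the model. The F3 models contain time, arm, their interaction and random intercepts. The weekly in-program symptom scores and the adverse events that would prompt withdrawal are not in them.

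**Working it through.** **Step 1: does 2.h reach beyond consent?** There are two readings.

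- If 2.h covers every study withdrawal, as its heading and lack of exceptions suggest, participants withdrawn by an investigator under E2 2.a lose all later data.
- If 2.h covers only withdrawal of consent, as its place after 2.g suggests, the protocol has no follow-up rule for the withdrawals that E2 2.a authorises.

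Either way the sections need reconciling. Removal from the program is a further undefined state: 2.h speaks of leaving the study, 2.b and 2.e of leaving the program.

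**Step 2: inputs for sizing.** The documents give no withdrawal rate, so there is no stated figure to reproduce.

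- Randomised: "N=7,884; of 146,000 initially screened" (A1). With 1:1 allocation, which is assumed because it is not stated, this is 7,884/2 = 3,942 per arm.
- Complete follow-up (F1): 3,154 high-risk + 3,154 clinical = 6,308, again 3,154 per arm at 1:1. Implied attrition is 1 − 6,308/7,884 = 20.0%.
- Assumed: true 2-year caseness p of 50% (30% as an alternative), no true effect, a share w of the intervention arm withdrawn, all of them cases, none withdrawn in control, and a complete-case analysis.

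**Step 3: shift in the intervention-arm case proportion.** The observed proportion is (p − w)/(1 − w), so the shift is (p − w)/(1 − w) − p. For example, at p = 0.5 and w = 0.01: 0.49/0.99 − 0.50 = −0.0051.

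| w | Participants (w × 3,942) | Shift at p = 50% (points) | Shift at p = 30% (points) | Type I error, two-sided 5% test |
|---|---|---|---|---|
| 0.25% | 10 | −0.1 | −0.2 | 5.1–5.3% |
| 1% | 39 | −0.5 | −0.7 | 7–9% |
| 2% | 79 | −1.0 | −1.4 | 13–24% |
| 5% | 197 | −2.6 | −3.7 | 55–89% |

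The last column uses a standard error of √(2p(1 − p)/3,154), ignoring clustering. At p = 0.5 this is 0.0126, so w = 1% gives 0.0051/0.0126 = 0.40 standard errors.

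**Step 4: relaxing one assumption.** If a share q of those withdrawn are cases, the shift is w(p − q)/(1 − w). At p = 0.5 and q = 0.75 this is −0.25 points at w = 1% and −0.5 at w = 2%, half the worst case.

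**Step 5: a yardstick.** F1 powers on an effect of 0.2 without naming the scale. Read as a log odds ratio from 50% control caseness, the intervention proportion is e^(−0.2)/(1 + e^(−0.2)) = 45.0%, a difference of 5.0 points; from 30% it is 26.0%, a difference of 4.0 points. On that assumed reading, the worst-case shift at w = 1% and p = 50% is about a tenth of the effect (0.5/5.0).

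**The case against.** The strongest reply is that 2.h is written in the active voice directly after a section confined to voluntary withdrawal, and stopping collection when consent is withdrawn is proper. That stands as a plausible reading, but it leaves investigator-initiated withdrawal without any follow-up rule.

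Several other points stand and limit the concern:

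- Worsening normally leads to referral, not removal. Intervention participants without improvement at 6 weeks are referred and may stay in the program, and participants of either arm still in the clinical range at 6 months or 2 years are offered referral (2.b, 2.e). A reader might infer that the sickest participants as a group lose their outcome data. The documents do not support that.
- Coach removal is from the program only, for continued imminent risk that the protocol presents as exceptional. The surveys run in Qualtrics, separately from the intervention platform. A reader might infer that removed users leave follow-up, but the text says neither that they leave nor that they stay.
- E2 2.a defines adverse events as unanticipated problems, which does not clearly include ordinary symptom worsening, and E2 2.b anticipates no significant events.
- Adverse events are also monitored at every follow-up and through other contact in both arms. More loss in the intervention arm is a reasoned possibility, not a documented fact.
- Intent-to-treat is not contradicted: withdrawn participants stay in their arm with the data already collected, and earlier visits inform the likelihood. Against implied attrition of about 20%, these withdrawals should be a small part of the missing data.

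**Conclusion.** The point holds as a gap in the rules with a possible bias, not as a demonstrated one. As written, the protocol lets investigators withdraw participants after adverse events, has a single withdrawal rule that ends data collection without exception, and relies on maximum likelihood alone for what is missing. The 2-year primary endpoint can therefore be lost for outcome-related reasons, possibly more often in the intervention arm.

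The size is unknown. Under worst-case assumptions at 50% caseness it is negligible at 0.25% withdrawn (about 0.1 points). It starts to matter at around 1–2% (0.5 to 1.0 points). Those figures assume that every withdrawn participant is a case, that none is withdrawn in control and that no information is recovered from earlier visits, so the true shift at a given rate should be smaller. The 5% row is an extreme that nothing in the documents suggests. The documents also do not support the stronger claim that the trial result will be biased.

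The change is still worth making because the endpoint affected is primary, follow-up data not collected cannot be recovered later, and the remedy is cheap.

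**What to change.** Reconcile D2 2.b, 2.e and 2.h with E2 2.a by defining three separate states:

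1. removal from, or stopping of, the program;
2. withdrawal initiated by an investigator;
3. withdrawal of consent for follow-up by the participant.

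Let 2.h end data collection only for the third. State that participants in the first two states are still invited to the 6-week, 6-month and 2-year surveys unless they decline, and stay in the analysis in their assigned arm. Record who initiated each withdrawal and why. E2 2.a already requires a detailed explanation of each study withdrawal, so the initiator is the main addition. These records would also support a sensitivity analysis for outcome-dependent missingness if the sponsor chooses to add one.

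The cost is revised protocol and consent wording and some extra survey invitations through the existing Qualtrics system. No change is proposed to when or whether anyone is withdrawn on clinical grounds.

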## ***D3 Study Intervention***

### **SilverCloud Health Guided Self-Help Mental Health Programs**

The SilverCloud Health platform provides three self-help guided interventions, one for each disorder (both for those with clinical symptoms and at high risk). The interventions were derived from evidence based guided self-help treatments that were efficacious in traditional efficacy trials, specifically for anxiety, depression, and EDs. Each session takes about 20 minutes. To maximize efficacy, key targets (i.e., decreased avoidance for anxiety disorders; increased behavioral activation for depression; decreased dietary restraint and weight/shape concerns for EDs; and decreased dysfunctional thoughts and increased use of Cognitive behavioral treatment skills for all three disorders) are addressed, which include the following content to address the targets: Anxiety: Psychoeducation on anxiety and avoidance, goal setting, self-monitoring and cognitive restructuring (to identify and alter negative automatic thoughts), exposure therapy, mindfulness/relaxation. Depression: Psychoeducation on the cognitive-behavioral theory of depression, goal setting, identifying and engaging in enjoyable activities (behavioral activation), emotion regulation and distress tolerance skills, self-monitoring and cognitive

---

restructuring (to identify and alter negative automatic thoughts). EDs: Psychoeducation on the cognitivebehavioral theory of EDs, self-monitoring, goal setting, meal planning and tracking, cognitive and behavioral strategies to improve body image, eating, and coping skills.

Participants completing the mobile intervention who screened positive or at high risk for 2 or more disorders (i.e., of depression, anxiety, and EDs) will be asked to choose a focus based on which problem is most bothersome or impairing to their everyday functioning, and will be assigned that program as their primary track. Incorporating participant preference in our approach is designed to enhance the students' involvement as stakeholders and to increase their engagement. As they progress through the intervention, they also will be assigned the components presumed to be essential to intervention effects for the comorbid disorder.

Participants completing the mobile intervention will receive the support from a coach. Their role includes supporting and enhancing user motivation; monitoring progress; facilitating goal setting and offering accountability; providing feedback on technique usage and encouraging practice; answering user questions; and monitoring for/responding to clinical risk. Communication with users is primarily via two-way, asynchronous messaging, with optional, supplementary phone calls to enhance goal setting. Coach messaging is done via a web-based "dashboard," and delivered to users within the SilverCloud Health app. Coaches have participants' baseline screen results so they can personalize treatment and help the user apply skills learned to comorbid problems. Moreover, coaches will monitor symptoms using the following assessments built into the SilverCloud Health programs:

- 1) For individuals with depression, depression is assessed weekly using an abbreviated version of the measure used for assessing depression at baseline (i.e., PHQ-2).
- 2) For individuals with anxiety, anxiety is assessed weekly using a short, validated measure of anxiety (i.e., GAD-2).
- 3) For individuals with eating disorders, weekly monitoring includes three questions based on the EDE-Q assessing eating disorder behaviors (i.e., binge eating, purging) and weight/shape concerns.

Note: When individuals have more than one of these problems, they complete weekly monitoring for each comorbidity.

If the coach feels the online program cannot adequately address comorbidity, participants are referred to appropriate campus/community resources.

The program will be accessible via smart phone app or their desktop. Program access will be password protected.

